9.1.2 SL-172154 Concentration Measures

SL-172154 concentration values will be sorted by sample collection day, and nominal time points in the listing. All SL-172154 concentration values including BLQ will be listed in the same precision as the source data.

SL-172154 concentration will be summarized for each nominal time point relative to the EOI. Standard summary statistics will be calculated (i.e., mean, standard deviation, median, minimum, maximum, coefficient of variation (CV%), geometric mean, geometric CV%).

9.1.3 SL-172154 PK Parameters

The PK parameters will be derived from the concentration-time data using the actual collection time from SOI. The PK parameters will be calculated by standard non-compartmental analysis (NCA) as data permits. At least one post-dose concentration at planned time of end of infusion or 0.5 hour post end of infusion is required for C_{max} calculation, and at least three consecutive post-dose concentrations are required for AUC parameter calculation.

Table 9 SL-172154 PK Parameters

C_{max}	Maximum observed concentration over a dosing interval
C_{trough}	Observed concentration at the end of a dosing interval.
T_{max}	Time of maximum observed concentration
AUC_{0-last}	The area under the serum concentration time curve, from time 0 to the last quantifiable concentration, calculated by a combination of linear and logarithmic trapezoidal methods (Linear up/log down method).

AUC _{0-inf}	Area under the serum concentration time curve from time 0 extrapolated to infinity, calculated as AUC _{last} + C _{last} /terminal elimination rate constant (λ_z). Reliability of AUC _{0-inf} values is contingent on the percent of the total area obtained by extrapolation: AUC _{0-inf} values with <20% of the total area coming from C _{last} / λ_z are considered acceptable. Any exceptions to the above procedures will be clearly documented/justified in the PK report.
AUC _{tau}	The area under the serum concentration time curve over the dosing interval, calculated by a combination of linear and logarithmic trapezoidal methods (Linear up/log down method).
%AUC _{ext}	Percentage of AUC _{0-inf} due to extrapolation from T _{last} to infinity
t _{1/2}	Terminal elimination half-life, estimated using the equation $[\ln(2)/\lambda_z]$
CL	Clearance; calculated as Dose/AUC _{0-inf} for C1D1 and Dose/AUC _{tau} for later time unless specified otherwise
V _Z	Volume of distribution, calculated as Dose/($\lambda_z * AUC_{0-inf}$) for C1D1 and Dose/($\lambda_z * AUC_{tau}$) for later time unless specified otherwise
AR _{AUC_{tau}}	Accumulation ratio of AUC _{tau} or AUC _{0-xx} (over the dosing interval), C1D15/C1D8 and C2D8/C1D8.
AR _{C_{max}}	Accumulation ratio of C _{max} (C1D15/C1D8 and C2D8/ C1D8).

The elimination rate constant (λ_z) will be determined if the log-linear terminal elimination phase is apparent and excludes C_{max}. The λ_z will only be considered reliable if the adjusted coefficient of determination (adj-R²) is greater than or equal to 0.8. Parameters dependent on λ_z (i.e., t_{1/2}, AUC_{0-inf}, AUC_{%ext}, CL, V_Z) will not be presented if λ_z cannot be estimated.

The following PK parameters will be calculated for diagnostic purposes and listed but not be summarized:

- λ_z lower: Lower limit of time (h) included in the calculation of λ_z
- λ_z N: Number of data points used in the calculation of λ_z
- λ_z upper: Upper limit of time (h) included in the calculation of λ_z
- Adjusted-R²: Regression coefficient for calculation of λ_z

All PK parameters will be listed and summarized for each PK sample collection day. For each of the PK parameters, except T_{max}, the following summary statistics will be calculated: median, minimum, maximum, arithmetic mean, standard deviation, CV%, geometric mean, and geometric CV%. For T_{max}, median, minimum, and maximum will be calculated. All PK parameters will be reported with the same precision as the source concentration data except that T_{max} and t_{1/2} will be reported with 2 decimal places and λ_z will be reported with at least 3 significant figures.

9.2 MIRV PK Analyses

All MIRV PK data analyses will be based on the MIRV PK population. Blood samples for MIRV PK will be collected at predose and EOI of Day 1 for each cycle and at PTV. MIRV concentration data will be summarized for each nominal time point relative to the EOI. Standard summary statistics will be calculated (i.e., mean, standard deviation, median, minimum,

maximum, CV%, geometric mean, geometric CV%). All MIRV concentration data will also be listed.

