To assess the pharmacokinetic profile of SL-172154 when administered with PLD or MIRV in subjects with platinum-resistant ovarian, primary peritoneal, or fallopian tube cancer	
 Maximum observed concentration (C_{max}), time at which the maximum concentration is observed (T_{max}), and minimum observed concentration (C_{min}) following single and multiple doses of SL-172154 Area under the serum concentration-time curve (AUC) Terminal elimination half-life ($t_{1/2}$), Clearance (CL) and Volume of Distribution (V_z), as data permit

Objective	Outcome Measure
To assess the pharmacokinetic profile of MIRV when administered with SL-172154 in subjects with platinum-resistant ovarian, primary peritoneal, or fallopian tube cancer	
 PK exposure evaluation of MIRV, total antibody, and payload (DM4 and S-methyl DM4)
Exploratory Objectives	
To identify and assess pharmacodynamic biomarkers associated with ovarian cancer or the mechanism of action of SL-172154, PLD, or MIRV following treatment with SL-172154 administered with PLD or MIRV in subjects with platinum-resistant ovarian, primary peritoneal, or fallopian tube cancer	
 Changes from baseline in select cytokines Changes in immune cell subsets CD47 and CD40 expression Target-associated regulatory networks Genomic alterations which may correlate with drug safety or efficacy
To explore the association of biological/clinical endpoints with PK parameters of SL-172154 administered with PLD or MIRV in subjects with platinum-resistant ovarian, primary peritoneal, or fallopian tube cancer	
 To assess the relationship between SL-172154 PK exposure and the anti-tumor activity and safety of SL-172154, if feasible
Estimate overall survival (OS)	
 OS: time from first dose to death

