3.6.2 Medications to be used with Caution

Please refer to the current listing of drugs that are cytochrome P450 (CYP450) substrates, including CYP3A4, CYP2D6 and P-glycoprotein (P-gp) substrates, at: <https://www.fda.gov/drugs/drug-interactions-labeling/drug-development-and-drug-interactions-table-substrates-inhibitors-and-inducers#table3-1>.

SL-172154

SL-172154 is a therapeutic protein that may induce the transient release of cytokines including IL-6 which in turn, may inhibit the activity of CYP450 enzymes including CYP3A4 activity [Evers, 2013]. Although not tested clinically, a drug-drug interaction may occur with the co-administration of medications that are CYP450 substrates. Drugs metabolized by CYP450 enzymes may have reduced clearance or an increase in half-life or peak plasma concentration and should be used with caution. There may be an increased risk of side effects for drugs that are CYP450 substrates. Where possible consider substitutions for these medicinal products if therapeutic effects cannot be monitored.

PLD

Doxorubicin is a major substrate of CYP3A4 and CYP2D6, and P-gp. Clinically significant interactions have been reported with inhibitors of CYP3A4 (e.g., ketoconazole, erythromycin, ciprofloxin), CYP2D6 (e.g., paroxetine, fluoxetine, and/or P-gp (e.g., verapamil), resulting in increased concentration and clinical effect of doxorubicin.

Inducers of CYP3A4 (e.g., phenobarbital, phenytoin, St. John's Wort) and P-gp inducers may decrease the concentration of doxorubicin. If possible, avoid concurrent use of doxorubicin with strong inhibitors and strong inducers of CYP3A4, CYP2D6, or P-gp.

MIRV

In vitro metabolism studies demonstrated that DM4 is predominantly metabolized by thiol s-methyltransferase to form S-methyl DM4, which is further metabolized into sulfoxide methyl-DM4. As S-methyl DM4 has been shown to be primarily metabolized by CYP3A, its exposure could potentially be increased in the presence of strong CYP3A inhibitors. Drinking greater than one serving (250 mL) of grapefruit juice per day should be avoided.

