u. **Post-Treatment Visit (PTV):** visit should occur 30 days (\pm 7 days) after the last dose of study treatment. If the subject is going to start a new anticancer therapy before the PTV due date, PTV should be conducted prior to starting the new therapy.

v. **Survival Follow-Up (SFU):** All subjects will be contacted after discontinuing study treatment to collect survival status. Subjects should be contacted every 3 months (± 14 days) from the PTV until death, withdrawal of consent, lost to follow-up or end of study. Contact may include clinic visit, telephone contact, email or mail, chart review, or obituary notice to document survival status. Initiation of any subsequent anti-cancer therapy should also be reported.

6.2.1 PK, ADA, Cytokines and Receptor Occupancy (SL-172154 + MIRV Dose Escalation and Dose Expansion Cohorts)

CYCLE 1	C1D1			C1D8								C1D9	C1D15						
	Predose ¹	EOI ²	2h post EOI	Pre-dose ¹	EOI ²	0.5h post EOI	1h post EOI	1.5h post EOI	2h post EOI	4h post EOI	6h post EOI		Pre-dose ¹	EOI ²	0.5h post EOI	1h post EOI	1.5h post EOI	2h post EOI	4h post EOI
Blood sample for SL-172154 PK ^{3,4,5,6}				X	X	X	X	X	X	X	X	X	X	X	X	X	X	X	X
Blood sample for SL-172154 ADA ⁶				X									X						
Blood sample for MIRV PK [D1 of each cycle] ⁶	X	X																	
Blood sample for MIRV ADA, neutralizing antibodies [D1 of each cycle] ⁶	X																		
Blood sample for cytokines ^{3,5} (during dose escalation and for approximately 25 subjects in dose expansion)				X					X			X	X					X	
Blood sample for Receptor Occupancy ^{3,5} (during dose escalation and for approximately 25 subjects in dose expansion)				X			X					X	X		X				

CYCLE 2	C2D8								C3D8 and onwards in every cycle ⁷
	Predose ¹	EOI ²	0.5h post EOI	1h post EOI	1.5h post EOI	2h post EOI	4h post EOI	6h post EOI	
Blood sample for SL-172154 PK ^{3,4,6}	X	X	X	X	X	X	X	X	
Blood sample for SL-172154 ADA ⁶	X								X

Abbreviations: ADA = anti-drug antibodies; C = cycle; D = day; EOI = end of SL-172154 infusion; IRR = infusion-related reaction; MIRV= mirvetuximab soravtansine; PK = pharmacokinetics

Note: Please refer to [Table 2](#) for infusion duration for the assigned SL-172154 dose

1. Predose samples should be collected within 60 minutes prior to the start of the MIRV infusion or the SL-172154 infusion.
2. EOI samples should be collected ± 5 min from the end of the MIRV infusion or the SL-172154 infusion.

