6.5.9 Local and Central Clinical Laboratory Assessments

Refer to the SOA (Section 6.1 and Section 6.2) for the timing and frequency of local laboratory tests performed.

Local Clinical Labs				
Hematology	Clinical Chemistry			
Hemoglobin	Blood urea nitrogen or Urea	Magnesium		
Hematocrit	Creatinine	Phosphorus		
Platelet Count	Glucose	Total Protein		
Red Blood Cell Count	Sodium	Albumin		
White Blood Cell Count	Potassium	Lactate dehydrogenase		
Mean Corpuscular Volume	Calcium	Bicarbonate or CO ₂		
	Aspartate aminotransferase	Total and direct bilirubin*		
	Alkaline phosphatase	Alanine aminotransferase		
Automated WBC Differential	Antiviral Testing	Thyroid		
Neutrophils	Hepatitis B: HbsAg / HBV core Ab	Thyroid stimulating hormone (TSH)		
Lymphocytes	Hepatitis C: HCV Ab / HCV RNA viral load	Free thyroxine 4		
Monocytes				
Eosinophils				
Basophils				
Coagulation		Serum/Urine Pregnancy Test		
Prothrombin time and International- normalized ratio	β-human chorionic gonadotropin			
Activated partial thromboplastin time				
Fibrinogen				
D-Dimer				
Other				
Ferritin and haptoglobin (Screening and Cycle 1 Day 9)				
C-reactive protein (Screening)				
Blood Type and Screen (Screening)				
ABO/Rh	Kell, Kidd	Duffy, MNS		
D, C, E	Direct antiglobulin test (DAT)	Antibody Screen		

* Both total and direct bilirubin assessments should be performed, but if required per the standard practices, direct bilirubin can be omitted when total bilirubin is normal.

Refer to the SOA (Section 6.1, Section 6.2, Section 6.1.1 and Section 6.2.1) for the timing and frequency of central laboratory tests performed. A separate SLM detailing the preparation, storage, and shipping requirements for these samples collected during the study will be provided.

Central Laboratory Tests	
Peripheral Blood	
Pharmacokinetics	SL-172154 serum concentration (all subjects) MIRV serum concentration [MIRV cohort only]
Immunogenicity	Anti-drug antibodies (ADA) to SL-172154 MIRV ADA [MIRV cohort only]

Protein analysis (serum)	Assessment of potential immune regulators such as cytokines
Receptor occupancy	Flow cytometry-based measurement for receptor occupancy of SL-172154 on CD47 and CD40 in select subsets of peripheral blood mononuclear cells
Tumor Tissue	
Ventana FOLR1 Assay	Confirmation of FR α positivity to meet eligibility criterion [MIRV Cohort only]

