11. CHANGE FROM PROTOCOL-SPECIFIED ANALYSES

There are no changes from the protocol-specified analyses.

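### The MIRV exposure outcome names four analytes but the plan provides for one, and the MIRV summaries mix reduced doses and delayed cycles

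*SAP*

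**What the plan says.** The outcome for the secondary objective on MIRV pharmacokinetics is "PK exposure evaluation of MIRV, total antibody, and payload (DM4 and S-methyl DM4" in Protocol Section 2, and SAP Section 2 repeats it.

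The central laboratory table in Protocol 6.5.9 has one matching entry: "MIRV serum concentration [MIRV cohort only". Protocol 9.2.6 provides for a summary of MIRV concentrations and names no other MIRV-related analyte. SAP 9.2 says "MIRV concentration data will be summarized for each nominal time point relative to the EOI". The only MIRV PK outputs in SAP 13 are Table 14.3.7.3b and Listing 16.2.5.5b, both for MIRV serum concentration. SAP 11 reads "There are no changes from the protocol-specified analyses".

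Protocol 6.2.1 schedules "Blood sample for MIRV PK [D1 of each cycle", at predose and end of infusion (EOI), with a further sample at the post-treatment visit (PTV). SAP 9.2 agrees: "Blood samples for MIRV PK will be collected at predose and EOI of Day 1 for each cycle and at PTV". SL-172154 is given on Days 8 and 15 of the 21-day cycle.

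Protocol 3.7.3.1 (Table 6) allows MIRV to be reduced from 6.0 to 5.0 to 4.0 mg/kg. Protocol Section 6 and the 6.2 footnotes allow a cycle to be extended when the next Day 1 is delayed. Protocol 6.6 moves PK sampling to the actual MIRV day. SAP 5.2 breaks tables down by SL-172154 dose level, uses the nominal visit and applies no visit windows.

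**The concern.** An outcome that names four analytes needs an assay, an analysis and an output for each. Here the chain stops at one. A study team working from these documents would finish with nothing to report on total antibody or either payload species, and the SAP's own statement on changes would not explain why.

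The part that is delivered has a separate weakness. A nominal-time-point summary of MIRV in later cycles combines subjects on different MIRV doses, and troughs taken at different times after the previous dose. A falling mean across cycles could be read as an effect of the combination when it reflects only dose reduction or delay.

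**Working it through.** The plan attaches no sample-size or power figure to this outcome, so the check is a count of analytes, a count of days, and the size of the mixing.

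**1. Analytes at each step**

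| Step | MIRV | Total antibody | DM4 | S-methyl DM4 |
|---|---|---|---|---|
| Outcome (Protocol 2, SAP 2) | yes | yes | yes | yes |
| Central laboratory table (Protocol 6.5.9) | yes | no | no | no |
| Analysis (Protocol 9.2.6, SAP 9.2) | yes | no | no | no |
| Table 14.3.7.3b, Listing 16.2.5.5b | yes | no | no | no |

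Four are named and one is carried through, so 4 − 1 = 3 have no specified route to a result.

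**2. Sampling against SL-172154 dosing, Cycle 1**

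- MIRV samples: Day 1 predose, Day 1 EOI, then Cycle 2 Day 1 predose, which is Day 22 if there is no delay.
- From the Day 8 SL-172154 dose to the next MIRV sample: 22 − 8 = 14 days.
- From the Day 15 dose: 22 − 15 = 7 days. From Cycle 2 the ±2-day dosing window makes this 5 to 9 days.

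Only the two Cycle 1 Day 1 samples precede SL-172154. The EOI sample gives an SL-172154-free reference for the peak. The predose sample precedes the first MIRV dose, so it is not a trough. The first trough, on Day 22, already follows two SL-172154 doses, and there is no MIRV-alone arm. Protocol 3.11 lets a subject stop SL-172154 and continue MIRV alone. Such troughs would be few, would come from selected subjects with earlier SL-172154 exposure, and are not separated in SAP 9.2.

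**3. Size of the mixing**

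*Dose.* Assume EOI concentration is proportional to dose.

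- 5/6 = 0.83, about 17% lower.
- 4/6 = 0.67, about 33% lower.

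*Interval.* The documents give no MIRV half-life, so half-lives (t½) of 3, 5 and 7 days are assumed. For a 7-day delay, also assumed, the trough is multiplied by 2^(−7/t½):

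- t½ 3 days: 2^(−2.33) = 0.20, about 80% lower.
- t½ 5 days: 2^(−1.4) = 0.38, about 62% lower.
- t½ 7 days: 2^(−1) = 0.50, 50% lower.

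An EOI value mainly reflects the dose just given, whereas a predose value reflects the previous dose and the time since it. The two sample types therefore need different dose labels.

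**The case against.** The strongest reply is that the outcome asks for an exposure evaluation and promises no AUC. The SL-172154 objective in the same table does name AUC, half-life and clearance, and the MIRV objective does not. EOI and trough are legitimate exposure measures under sparse sampling, so the MIRV part is delivered. This stands. A reader might infer that the outcome cannot be delivered at all, or that two points per cycle fail it for lack of an AUC. The documents support neither reading.

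A reader might also infer that the sampling misses the period after SL-172154. It does not, because every sample from Cycle 2 Day 1 predose onward follows it. Nor is the trough blind. In a one-compartment illustration with the same assumed half-lives, a 20% fall in MIRV clearance from Day 8 to Day 22 multiplies the trough by 2^(0.2 × 14/t½), a rise of 91%, 47% and 32%. The limit is attribution, since the trial plans no SL-172154-free trough.

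A third tempting reading is that the plan fails to test a drug interaction. Protocol 3.6.2 says cytokines released after SL-172154 "may inhibit the activity of CYP450 enzymes including CYP3A4 activity" and that "S-methyl DM4 has been shown to be primarily metabolized by CYP3A". That is precautionary text, described there as untested clinically. No interaction objective is stated. Extra mid-cycle samples would still lack a MIRV-alone reference.

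On SAP 11, SAP 9.2 does match Protocol 9.2.6, so the gap begins inside the protocol, between Section 2 and 9.2.6. The SAP nevertheless repeats the four-analyte outcome and leaves the gap unrecorded. Sample details are also deferred to a Study Lab Manual that is not part of these documents, so assays may exist. The supportable statement is that neither the protocol nor the SAP specifies them.

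On mixing, every Cycle 1 MIRV dose is planned at 6.0 mg/kg, so Cycle 1 EOI and the Cycle 2 predose value are free of dose reduction. All concentrations and MIRV administrations are listed by subject. Both points are fair, but a listing does not correct a misleading later-cycle summary.

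**Conclusion.** The point holds in limited form. Three of the four named analytes have no assay, analysis, table or listing specified in either document, and SAP 11 is silent on this. MIRV exposure is confined to EOI and trough, and a trough effect cannot be attributed to SL-172154 within this trial. Later-cycle MIRV summaries mix doses and intervals. The illustrative size is 17% to 33% at EOI for dose reduction, assuming proportionality, and 50% to 80% at trough for a one-week delay under the assumed half-lives.

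The outcome is descriptive and secondary, with no hypothesis or sample size attached, so the consequence is an unreported outcome and a possible misreading of later cycles. It should be corrected before database lock. It does not threaten the primary safety objective.

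**What to change.** (a) If total antibody, DM4 and S-methyl DM4 are being assayed on the existing Day 1 and PTV samples, add them to the central laboratory table in Protocol 6.5.9, to SAP 9.2, and to the SAP 13 tables and listings. If they are not, restate the outcome in both documents as MIRV predose and EOI concentration, and record the change in SAP 11.

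(b) In SAP 9.2, summarise MIRV by the MIRV dose actually received, or dose-normalised. Use the current dose for EOI values and the preceding dose for predose values. Summarise predose values only where the preceding interval was about 21 days, and list the others separately.

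The same edit can reconcile the matrix, which is plasma in Protocol 9.2.6 and serum in Protocol 6.5.9 and the SAP outputs.

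No new visit or blood draw is needed. Either branch of (a) changes protocol text and so needs an amendment with ethics review, while (b) is SAP wording and programming. The price of (b) is smaller cells in later cycles. The price of the restatement in (a) is a narrower claim.

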10. IMMUNOGENICITY

10.1 SL-172154 ADA Data Analyses

All SL-172154 ADA data summaries and analyses will be performed for subjects included in the SL-172154 immunogenicity population.

SL-172154 treatment induced ADA is defined as positive sample after first SL-172154 dose for subjects with negative or missing ADA at first SL-172154 predose. Sustained ADA response is defined as treatment induced ADA in ≥ 2 consecutive samples without a subsequent negative sample or in the last sample. Persistent ADA response is defined as treatment induced ADA in ≥ 2 samples, with the first and last samples (irrespective of any negative in between) separated by ≥ 16 weeks, or only in 1 sample but the last sample, or only in 1 sample but less than 16 weeks before a negative last sample.

A summary of SL-172154 ADA at first SL-172154 predose and during the study will be provided. The summary of onset and duration of treatment induced ADA during the study will also be provided in a table. All SL-172154 ADA data along with any available Nab data will be listed for all subjects in Immunogenicity population.

10.2 MIRV ADA Data Analyses

All MIRV ADA data summaries and analyses will be performed for subjects included in the MIRV immunogenicity population.

MIRV treatment induced ADA is defined as positive sample after C1D1 first dose for subjects with negative or missing ADA at C1D1 predose. The summary of MIRV ADA at C1D1 predose and treatment induced ADA during the study will be provided. All MIRV ADA data along with available Nab data will be listed for all subjects in Immunogenicity population.

11. CHANGE FROM PROTOCOL-SPECIFIED ANALYSES

There are no changes from the protocol-specified analyses.

13. APPENDIX: LIST OF TABLES, FIGURES AND LISTINGS

The table, figure and listing titles proposed in this section apply to both Regimen (SL-172154 + PLD) and Regimen (SL-172154 + MIRV), unless specified otherwise. The regimen will be indicated in the numbering and output titles. Regimen (SL-172154 + PLD) output numbering will end with “a”, and Regimen (SL-172154 + MIRV) output numbering will end with “b”. In titles where there is “PLD” wording for Regimen (SL-172154 + PLD), “PLD” will be replaced with “MIRV” for Regimen (SL-172154 + MIRV) outputs. Additional details for Regimen (SL-172154 + MIRV) outputs will be specified in the table, figure, and listing shells as necessary. If the study is prematurely terminated, select tables, figures, and listings as agreed upon by the study team will be produced for the abbreviated clinical study report (aCSR).

